4.3.3 Study design rationale

This is the first study of isatuximab in combination with cemiplimab. To evaluate the safety and clinical activity in RRMM, the study is designed in 2 parts.

The Phase 1 part is to confirm the feasibility of the isatuximab / cemiplimab combination and select a recommended dose for Phase 2. The maximum tolerated dose (MTD) defined as the highest dose intensity at which 0 out of 3 or no more than 1/6 patients have DLT. Given the promising early signs of the activity and the acceptable safety profile of each of the two antibodies, and that MTD has not been reached in either one as monotherapy with isatuximab 20 mg/kg QW and cemiplimab 10 mg/kg, no typical dose escalation is planned. A cohort of 3 patients will be treated at starting dose of 10 mg/kg QWx4 followed by Q2W for isatuximab and 250 mg Q2W for cemiplimab, which have been shown to be clinically active with an acceptable safety profile both as monotherapy and in combinations with other standard therapies. If necessary, dose will be de-escalated with typical 3+3 design rule.

The Phase 2 part is a proof of concept study to determine the efficacy of the combination of isatuximab and cemiplimab in RRMM patients using ORR as primary endpoint, and to further evaluate the safety of the combination therapy. The efficacy of single-agent isatuximab and other CD38 drugs is well established in patients with RRMM who have received at least three prior lines of therapy including a PI and an IMiD or whose disease is double refractory to PI and IMiD (42, 43). A control arm consisting of isatuximab given as a single agent will be used in Phase 2 to characterize the treatment benefit and risk profile when cemiplimab is combined with isatuximab, and will serve to detect the risk ascribable to cemiplimab when it is combined to isatuximab in RRMM. To ensure that the most effective and safe dose of cemiplimab will be used in this study, two different doses will be assessed if it is permitted based on the MTD finding from Phase 1. Patients will be randomized in the 3 study arms of Phase 2.

Patients will be followed until progression of disease (PD) or death for a maximum of 2 year after last patient is treated. This will allow the study to have a proper evaluation of the combination in term of PFS and OS.

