6.5 DOSE DELAYS/ MODIFICATIONS

6.5.1 General rules

Dose modifications are permitted according to the guidelines described in this section.

Dose modifications different from those stated in the protocol should only be made in consultation with the Sponsor unless required for immediate patient safety.

Dose adjustment and/or cycle delay are permitted in case of toxicity. Dose adjustments will be made according to the worst grade of toxicity observed within a cycle. If a patient experiences several toxicities and there are conflicting recommendations, the most conservative dose adjustment recommended should be followed. Once a dose has been decreased, intra-patient re-escalation back to the previous dose level is not permitted.

Administration of the study treatment will be discontinued in the event of a TEAE that persists despite appropriate dose modifications or any other AE that, in the opinion of the Investigator, warrants discontinuation.

If one of the 2 drugs (cemiplimab or isatuximab) is prematurely permanently discontinued, the other drug can be continued until disease progression, unacceptable adverse reaction, patient's refusal of further treatment, or in the absence of a clear benefit from therapy. The end of treatment assessment in this case will be 30 days after the date of the last IMP administration.

All changes to study treatment administration must be recorded in the eCRF.

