1.1 STUDY DESIGN AND RANDOMIZATION

The study is conducted in 2 parts:

- The Phase 1 (lead in) part was to confirm the feasibility of the isatuximab/cemiplimab combination using 3 + 3 dose de-escalation design. The Phase 1 part of the study was completed at time of writing of this SAP. Three patients were enrolled at DL1 (isatuximab 10 mg/kg once weekly (QW) for four weeks followed by once every two weeks (Q2W) + cemiplimab 250 mg (Q2W) and no patient had DLT.
- The Phase 2 part is to further evaluate the safety, efficacy and PK of the combination versus isatuximab monotherapy. Based on the evaluation of the results from the Phase 1 part of the study, patients are randomized in the Phase 2 part of the study in 1 of the 3 arms using an interactive response technology (IRT) in a 1:1:1 ratio:
 - Arm 1 (control): isatuximab 10 mg/kg QWx4 followed by Q2W (QW/Q2W),
 - Arm 2 (DL1): isatuximab 10 mg/kg QW/Q2W + cemiplimab 250 mg Q2W,
 - Arm 3 (DL-1): isatuximab 10 mg/kg QW/Q2W + cemiplimab 250 mg Q4W.

The duration of the study for a patient will include a period for screening of up to 21 days. Patients will continue treatment until disease progression, unacceptable adverse events, consent withdrawal, or any other reason. After the last dose of study treatment (isatuximab or cemiplimab), the post-treatment follow up period include an extended safety follow-up period of 90 days, and further follow up beyond 90 days after last treatment until death or study cutoff date, whichever occur first.

A maximum of 105 patients (35 patients per arm) will be randomized in the Phase 2 randomization part. Details on study design can be found in Protocol Section 6.

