1.2 OBJECTIVES

1.2.1 Primary objectives

The primary objectives are:

- To determine the safety and tolerability of the combination of isatuximab and cemiplimab.
- Phase 2 only: to compare the overall response rate (ORR, defined as complete response[CR] + very good partial response[VGPR] + partial response [PR]) of the combination of isatuximab and cemiplimab versus isatuximab alone in patients with RRMM based on International Myeloma Working Group (IMWG) criteria.

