2.1.4 Safety endpoints

The safety analysis will be based on the reported AEs and other safety information, such as clinical laboratory data, vital signs, ECG and ECOG performance status ([Section 1.4](#)).

Observation period

The observation period will be divided into 3 periods: pre-treatment, on-treatment, and post-treatment including the extended safety follow-up period.

- The **pre-treatment period** is defined as the time from when the patient gave informed consent and the start of study treatment administration.
- The **on-treatment period** is defined as the time from the first dose of study treatment up to 30 days after the last dose of study treatment.
- The **post-treatment period** is defined as the time starting the day after the end of the on-treatment period up to the end of the study (as defined in the protocol).
 - The **extended safety follow-up period** is defined as the time period from 31 days after the last dose of study treatments to 90 days after the last dose of study treatments.

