Sorting within tables will ensure the same presentation for the set of all AEs within the observation period (pre-treatment, on-treatment, and post-treatment). For that purpose, the table of all TEAEs presented by SOC and PT sorted by the internationally agreed SOC order and decreasing frequency of PTs within SOCs will define the presentation order for all other tables unless otherwise specified. Sorting will be based on the incidence of AEs of the isatuximab QW/Q2W plus cemiplimab Q2W arm.

Overview of TEAEs

An overview of TEAEs including the number (%) of patients with the following treatment emergent events will be provided:

- TEAE.
- TEAE of Grade ≥ 3 .
- TEAE of Grade 3-4.
- TEAE of Grade 5 (any TEAE with fatal outcome during the on-treatment period).
- Treatment emergent SAE.
- TEAE leading to definitive study treatment discontinuation, ie, discontinuation of isatuximab in control arm, and discontinuation of isatuximab and cemiplimab in combination arms.
- TEAE leading to premature discontinuation (only applicable to combination arms)
 - TEAE leading to premature isatuximab discontinuation, ie, discontinuation of isatuximab before cemiplimab,
 - TEAE leading to premature cemiplimab discontinuation, ie, discontinuation of cemiplimab before isatuximab.
- AESI
 - IR of Grade ≥ 2 .
- Treatment-related TEAE (related to either isatuximab or cemiplimab).
- Treatment-related TEAE of Grade ≥ 3 .
- Serious treatment-related TEAE.

Other significant adverse events

Infusion reactions

IR analyses will be done by including all the adverse events regardless of relationship to isatuximab, cemiplimab or NIMP. Unless otherwise described, the presentation strategy is described in [Table 7](#).

- Number (%) of patients experiencing IRs (as a diagnosis, no symptoms) according to investigator reported AEs presented by primary SOC and PT (both sorted by decreasing order of frequency) will be summarized by grades (all grades and Grade ≥ 3).
- Description of the IR diagnoses (using the diagnosis reported and excluding symptoms)
 - Worst grade,
 - Action taken with isatuximab and cemiplimab,
 - Number (%) of patients with only 1, ≥ 1 , ≥ 2 , ≥ 3 , ≥ 4 and ≥ 5 episodes,
 - Number (%) of patients with first occurrence of IR at the first infusion and subsequent infusions,
 - Number (%) of patients with IR at the first and subsequent infusions,
 - Number (%) of patients with at least two episodes of IRs at the same infusion,
 - Day of onset from infusion,

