SOC and PT	
 Primary SOC: internationally agreed order PT: decreasing order of frequency of Isa + CemQ2W arm 	
By treatment arms (and all patients if Phase 1): n (%) of patients with any event and n (%) of patients with event of Grade ≥3
	
 All TEAEs TEAEs occurring in ≥5% of the patients (in any group for Phase 2) Drug-related TEAEs Serious TEAEs Drug related serious TEAEs TEAEs leading to isatuximab discontinuation TEAEs leading to cemiplimab discontinuation TEAEs leading to dose interruption of isatuximab TEAEs leading to dose interruption of cemiplimab TEAEs leading to dose delay of isatuximab TEAEs leading to dose delay of cemiplimab TEAEs leading to dose reduction^a of isatuximab TEAEs leading to dose reduction^a of cemiplimab Pre-treatment AEs; Serious pre-treatment AEs Post-treatment AEs; Serious post-treatment AEs

MedDRA variables	Sorting	Layout	Events
SOC and PT	
 Primary SOC: internationally agreed order PT: decreasing order of frequency of Isa + CemQ2W arm 	
By treatment arms (and all patients if Phase 1): n (%) of patients with any event and n (%) of patients with event of Grade ≥ 3
	
IR analysis:
 
 IR diagnosis (as reported by investigator) Symptoms of IR (as reported by investigator) TEAEs (related; regardless of relationship) within 24 hours from the start of each infusion TEAEs (related; regardless of relationship) from the selected CMQ within 24 hours from the start of each infusion TEAEs (related; regardless of relationship) from the selected CMQ (not limited to those occurring within 24 hours from the start of each isatuximab infusion)
SOC and PT	
 Primary SOC: internationally agreed order PT: decreasing order of frequency of Isa + CemQ2W arm 	
By treatment arms (and all patients if Phase 1): n (%) of patients with any event and n (%) of patients with event of Grade ≥ 3
	
irAE analysis:
 
 irAE reported as AESI by investigator AEs as defined by irAE selected grouping of AEs occurring during the treatment emergent and extended safety follow up periods (related to cemiplimab; regardless of relationship) AEs occurring during the treatment emergent and extended safety follow up periods (related to cemiplimab; regardless of relationship)

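### The adverse-event tables give only crude percentages of patients over a window tied to last dose, so unequal treatment duration would be mixed, in either direction, with the cemiplimab risk the control arm is meant to show

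*Protocol*

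**What the plan says.** Safety is a primary objective: "To determine the safety and tolerability of the combination of isatuximab and cemiplimab" (SAP 1.2.1). Protocol 4.3.3 gives the control arm a comparative role in it: the arm "will serve to detect the risk ascribable to cemiplimab when it is combined to isatuximab in RRMM".

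Treatment has no fixed length in any arm: "Patients will continue treatment until disease progression, unacceptable adverse events, consent withdrawal, or any other reason" (SAP 1.1). If one of the two drugs is stopped early, "the other drug can be continued until disease progression" (Protocol 6.5.1); this can arise only in the combination arms.

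The window in which an event counts as treatment-emergent is "defined as the time from the first dose of study treatment up to 30 days after the last dose of study treatment" (SAP 2.1.4). SAP 2.4.5.2 then states: "An overview of TEAEs including the number (%) of patients with the following treatment emergent events will be provided". The layout in every row of Table 7 is "n (%) of patients with any event and n (%) of patients with event of Grade ≥3".

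Some outputs use other windows:
- Immune-related events are counted through the extended safety follow-up, to 90 days after last dose (SAP 2.1.4.1).
- Some infusion-reaction tables use 24 hours from the start of each infusion (SAP 2.4.5.2).
- Deaths are also counted within 60 days of first dose (SAP 2.4.5.3).

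Duration of exposure is summarised in its own tables (SAP 2.4.3) and is not used as a denominator for adverse events. Neither document plans an exposure-adjusted rate, a time-to-first-event or cumulative-incidence analysis, a TEAE table over a common fixed period, or an interval for a between-arm safety difference.

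**The concern.** A crude percentage depends on the event rate and on how long patients are watched. Here the watching time ends a fixed interval after last dose, so it moves with treatment duration. Two mechanisms could make duration differ by arm. The trial is sized on a response rate of 50% versus 20% (SAP 1.3), and treatment stops at progression, so a combination that works could be given for longer. Toxicity on the combination could instead shorten treatment. In the first case equal hazards look like added toxicity; in the second, part of a real excess is hidden. At stake is the reading of the one randomised contrast meant to separate cemiplimab risk from that of isatuximab.

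**Working it through.** **The plan's own figure.** The only numerical design figure near this point is the 79% power for response. It reproduces at 79.1% (exact one-sided Fisher test, 35 per arm, 20% versus 50%, alpha 0.05). It does not bear on safety, for which the documents give no expected rates or durations. Everything below is therefore illustrative.

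**Assumed inputs (not in the documents).** A constant first-event hazard λ, equal in both arms, of 0.05, 0.10 or 0.15 per month; exponential time on treatment with median 4 months in control and 6 months in a combination arm.

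**Input from the SAP.** A tail of 30 days after last dose, taken as 1 month.

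**Formula, no data cutoff.** With μ = ln 2 / median, crude incidence = 1 − exp(−λ × 1) × μ/(μ + λ).

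For λ = 0.05 and median 4: μ = 0.1733, so 1 − 0.9512 × 0.1733/0.2233 = 26.2%. For median 6: μ = 0.1155, so 1 − 0.9512 × 0.1155/0.1655 = 33.6%.

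| λ per month | Median 4 | Median 6 | Difference, no cutoff | Difference, cutoff with 12-month accrual | Difference, 6 months' follow-up for all |
|---|---|---|---|---|---|
| 0.05 | 26.2% | 33.6% | 7.4 | 4.4 | 1.8 |
| 0.10 | 42.6% | 51.5% | 8.9 | 6.2 | 3.0 |
| 0.15 | 53.9% | 62.6% | 8.7 | 6.8 | 3.7 |

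Differences are in percentage points. The last two columns close each patient's window at the earlier of 1 month after treatment end and the data cutoff. The first of them uses the primary cutoff, 6 months after the last patient's first dose (SAP 2.4.4), and assumes uniform accrual over 12 months. The second gives every patient only 6 months, which is the lower end.

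**Limits.** With equal medians the difference is 0. With the medians exchanged, so that the combination has 4 months and control 6, the same figures appear with the opposite sign. The true hazard difference is zero throughout, and the first-event rate per patient-month equals λ in both arms.

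**When the hazard is not constant.** Assume 0.25 per month in month 1 and 0.05 after, identical in both arms. The first-event rate is then 0.090 per patient-month at median 4 and 0.082 at median 6. The longer-treated arm looks about 10% safer, because later low-risk time dilutes its rate. An exposure-adjusted rate alone can thus mislead the other way.

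**Precision.** The 95% half-width for a crude difference at 35 per arm is 1.96 × √[p₀(1 − p₀)/35 + p₁(1 − p₁)/35]. For the three rows this is 21.4, 23.3 and 23.0 points.

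**The case against.** The strongest reply has four parts.

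1. The observation window is defined identically in all arms, and neither document says how long treatment will last in any of them. A reader might infer that the window does differ by arm and that longer treatment will therefore appear as cemiplimab toxicity. The documents do not support that: only the realised length can differ, and the direction is open. This part stands in full.

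2. Not every safety output uses the window to 30 days after last dose. The 60-day death count does not depend on treatment duration, and the 24-hour infusion tables are anchored to infusions. This also stands, but only in part. The 90-day immune-related window still moves with last dose, and the 24-hour tables still accumulate with the number of infusions. Tables restricted to cemiplimab-related events rest on causality judgements that have no counterpart in the control arm. Exposure summaries would let a reader notice an imbalance but not correct for it.

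3. The safety objective is descriptive, the SAP makes analyses descriptive unless stated otherwise (2.4), and the study has 35 patients per arm. The artefact computed above lies well inside the sampling error of a crude difference. That limits how much the point matters. It does not remove it, because Protocol 4.3.3 states a between-arm purpose and a bias remains a bias when the interval is wide.

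4. A constant-hazard rate can favour the longer-treated arm when events come early, which is plausible with weekly isatuximab in Cycle 1. This is correct. It is a reason to add a fixed-time measure and not to let the rate replace the percentages.

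**Conclusion.** The point holds conditionally. The planned TEAE contrast cannot separate duration of treatment from cemiplimab effect if durations differ, and nothing in the SAP would adjust for it. Under the assumptions shown, the size is about 7 to 9 points without a cutoff and about 2 to 7 points with one.

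A reader might choose wider durations, such as medians of 3 versus 7 months, and report 15 to 18 points. The documents do not support that contrast: it does not follow from response rates of 20% and 50%, and the figure ignores the data cutoff. It should not be quoted as the expected bias.

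This is a low-cost improvement to how the safety comparison is reported, not a flaw that invalidates the safety tables.

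**What to change.** In SAP 2.4.5.2, keep all the n (%) tables and add one supplementary table by arm. Its rows are Grade ≥3 TEAEs, serious TEAEs, fatal TEAEs, treatment-related Grade ≥3 TEAEs, and immune-related events over their own window. For each row give:

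- the first-event rate: patients with a first event divided by patient-months to first event or end of the observation period;
- the cumulative incidence of first event at a common fixed time from first dose, set in advance;
- for both measures, the difference of each combination arm versus control with a 95% confidence interval.

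State how patients whose observation ends before the fixed time are handled. Censoring them there, with death as a competing event, keeps the estimate from depending directly on duration. Counting end of treatment as a competing event would bring that dependence back.

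Add a sentence that statements on cemiplimab risk draw on this table together with the n (%) tables, not in place of them. Where events are front-loaded, rely on the fixed-time cumulative incidence. Leave infusion reactions as n (%).

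The cost is one SAP paragraph and one table from dates already collected, with no change to conduct. The drawbacks are the constant-hazard assumption behind the rate and intervals that will be wide at 35 per arm.

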5 STUDY OBJECTIVES

5.1 PRIMARY OBJECTIVE(S)

- To determine the safety and tolerability of the combination of isatuximab and cemiplimab.
- Phase 2 only: To compare the overall response rate (ORR, defined as CR+VGPR+PR) of the combination of isatuximab and cemiplimab versus isatuximab alone in patients with RRMM based on International Myeloma Working Group (IMWG) criteria (44).

5.2 SECONDARY OBJECTIVE(S)

- To determine the following efficacy measurements (Phase 2 only):
 - Clinical benefit rate (CBR, CR + VGPR + PR + Minimal response [MR]),
 - Duration of response (DOR),
 - Time to response (TTR),
 - Progression free survival (PFS),
 - Overall survival (OS).
- To determine the pharmacokinetic profile of isatuximab and cemiplimab when given in combination.
- To assess the immunogenicity of isatuximab and cemiplimab when given in combination.

5.3 EXPLORATORY OBJECTIVE(S)

- To explore the minimal residual disease (MRD) in patients achieving a CR.
- To assess the relationship between immune phenotypes, immune regulatory marker expression, adaptive immune response and parameters of clinical response.
- To explore central/effector memory T cell proliferation.

6 STUDY DESIGN

6.1 DESCRIPTION OF THE STUDY

This is a Phase 1/2 study to evaluate the safety, tolerability, efficacy and PK of isatuximab in combination with cemiplimab in RRMM.

The study will be conducted in 2 parts:

- The Phase 1 (lead in) part is to confirm the feasibility of the isatuximab / cemiplimab combination.
- The Phase 2 part will further evaluate the safety, efficacy and PK of the combination versus isatuximab monotherapy. Patients will be randomized in 1:1:1 in 3-arms or 1:1 in 2-arms study using an IRT.

Isatuximab and cemiplimab are defined in this protocol as “study treatments”.

6.2 PART 1

6.2.1 Starting dose and dose de-escalation design

Given the promising early signs of anti-cancer activity and the acceptable safety profile of each of the two antibodies (no MTD has been reached with either one as monotherapy), the starting dose will be 10 mg/kg QW for 4 weeks followed by Q2W for isatuximab and 250 mg Q2W for cemiplimab.

Dose de-escalation will be performed if necessary as defined in the [Table 1](#) below:

Table 1 - Treatment dose and schedule

Dose level	Isatuximab	Cemiplimab
Dose level 1 (DL1)	10 mg/kg QWx4 >Q2W	250 mg Q2W
Dose level -1 (DL-1)	10 mg/kg QWx4 >Q2W	250 mg Q4W
Dose level -2 (DL-2)	10 mg/kg Q2W	250 mg Q4W

Patients will continue treatment until disease progression, unacceptable adverse events, consent withdrawal, or any other reason.

At dose level 1 (DL1), 3 patients will be enrolled for DLT evaluation in Cycle 1:

- If 0/3 patient has DLT, no more patients will be enrolled in Phase 1, and DL1 will be the recommended Phase 2 dose (RP2D).
- If 1/3 patients has DLT, additional 3 patients will be enrolled at DL1 for DLT assessment:
 - If a total of 1/6 patient has DLT at DL1, the DL1 will be the RP2D,

- If a total of $\geq 2/6$ patients have DLT at DL1, dose will be de-escalated to dose level minus 1 (DL-1).
- If $\geq 2/3$ patients have DLT, dose will be de-escalated to dose level minus 1 (DL-1).

At DL-1, the same DLT observation rule will be applied for selecting a RP2D and for dose de-escalation.

At DL-2, the same DLT observation rule will be applied for selecting a RP2D. If $\geq 2/6$ patients have DLT, study committee will analyze all the data collected up to this point and determine whether the study is to be terminated without proceeding to Phase II or if alternative doses and schedules could be further examined in Phase I, or changes in the study design could be made based on the perceived benefit/risk to patients and on the PK results.

In Case 2 DLTs are observed before completion of enrollment no additional patients will be enrolled. Enrollment of patients within and between cohorts are staggered by at least 3 days.

For DLT definition, see [Section 9.1.1](#).

The DLT observation period is 1 cycle (28 days). However, all AEs during treatment, unless due to disease progression or an obviously unrelated cause, will be taken into consideration by the Study Committee for the determination of the MTD and RP2D.

The NCI CTCAE version 4.03 [Appendix C](#) will be used to assess the severity of AE, causal relationship is to be determined by the investigator. The DLTs will be confirmed by the Study Committee.

